2.4.7.2 Immunogenicity impact on PK

Immunogenicity impact on PK analysis may be explored, depending on the ADA prevalence.

A descriptive statistics of C_{trough} as described above will be provided at each cycle in the subset of negative patients by cohort and possibly overall where positive or inconclusive patients will be observed.

A graphical representation of individual C_{trough} profile will be provided throughout the course of treatment by cohort and possibly overall where positive or inconclusive patients will be observed. Positive patients profile will be highlighted (eg, color or bold) and the concentration of isatuximab and REGN2810 at the same time as ADA positive result will be notified.

2.4.8 Analyses of biomarker variables

The biomarker variables will be summarized by clinical group (eg, DCR ≥ 6 months for mCRPC patients vs. others) and overall. Graphics will be provided as appropriate. The biomarker variables include, but not limited to, the following variables:

- FCGR3A types: F/F, F/V, V/V and missing,
- CD38 expression
- PDL1 expression

Additional biomarker analysis may be conducted in an exploratory manner. Additional analysis, not specified in the protocol but related to the drug action and/or effect of isatuximab/REGN2810, may be conducted on remaining samples pending evolving literature.

2.4.9 Analyses of quality of life/health economics variables

Not applicable.

2.4.10 Further therapy after discontinuation of investigational medicinal product administration during the study

A listing of further therapy after discontinuation of investigational medicinal product administration during the study may be provided.

2.5 DATA HANDLING CONVENTIONS

2.5.1 General conventions

The following formulas will be used for computation of parameters.

Creatinine clearance (eGFR) using the equation of MDRD formula:

$$\text{GFR} = 175 \times (\text{Scr})^{-1.154} \times (\text{Age})^{-0.203} \times (0.742 \text{ if Female}) \times (1.212 \text{ if African American})$$

with serum creatinine in mg/dL and age in year.

Corrected calcium formula:

$$\text{Corrected Calcium (mmol/L)} = \text{Serum Calcium (in mmol/L)} + 0.8 (4 - \text{serum albumin [in g/dL]})$$

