2.1.4.5 Laboratory safety variables

Clinical laboratory data consists of blood and urine analysis including hematology, biochemistry and urinalysis. Clinical laboratory values will be converted into standard international units that will be used in all listings and tables.

Parameters measured on the day of the first study treatment infusion will be considered as part of the baseline measurements.

For laboratory safety variables, the treatment period is defined as the time from the first dose of study treatment (irrespective of treatment) administration to the last dose of study treatments + 30 days.

Blood and urine samples for clinical laboratories parameters will be taken as defined in the study flow charts and as clinically indicated. The laboratory parameters will be classified as follows:

- Hematology
 - **Hemoglobin and coagulation:** hemoglobin, hematocrit, red blood cell (RBC) platelet counts, prothrombin time or international normalized ratio (INR) and activated partial thromboplastin time (PTT)
 - **White blood cells (WBCs):** WBC count, leukocytes, neutrophils, lymphocytes, monocytes, basophils, eosinophils
- Biochemistry
 - **Metabolism:** fasting glucose, total protein
 - **Electrolytes:** sodium, potassium, chloride, calcium, albumin, magnesium, phosphate, bicarbonate/carbon dioxide

- **Renal function:** uric acid, serum creatinine, estimated creatinine clearance by modified diet in renal disease (MDRD) formula, urea or blood urea nitrogen (BUN)
- **Liver parameters:** alanine aminotransferase (ALT), aspartate aminotransferase (AST), alkaline phosphatase, total and direct bilirubin, lactate dehydrogenase (LDH)
- **Hormonal:** thyroid stimulating hormone (TSH) and free T4
- Urinalysis
 - Quantitative or semi-quantitative urinalysis: RBC, protein, glucose, pH, ketone, bilirubin, leukocytes, nitrates and specific gravity

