2.4.6.4 Analyses of laboratory variables

Each laboratory test result will be graded by CTCAE criteria (version 4.03), when applicable. For hematological parameters and for some biochemistry parameters, Sanofi sponsor generic normal ranges will be used for the grading of laboratory abnormalities (see list of parameters in [Table 6](#) and [Table 7](#)). For other biochemistry parameters (eg, for hepatic parameters), grading will be derived using the local laboratory normal ranges.

The number (%) of patients with abnormal laboratory tests at baseline and during the on-treatment period will be presented by all grades and each grade. For patients with multiple occurrences of the same laboratory variable during the on-treatment period, the maximum grade (worst) per patient will be used.

The denominator used for percentage calculation is the number of patients with at least 1 evaluation of the laboratory test during the considered observation period.

When appropriate, the summary table will present the frequency of patients with any grade of abnormal laboratory tests and with Grade 3-4 abnormal laboratory tests.

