7 LIST OF APPENDICES

Appendix A Generic ranges for hematological and biochemistry parameters

Table 6 - Generic ranges for hematological parameters

Test	Gender	Unit	Lower/Upper limit of normal
Hemoglobin	F	g/L	120 - 160
Hemoglobin	M	g/L	135 - 175
Lymphocytes		109/L	1-2
Neutrophils		109/L	1.8 – 3.15
Platelets		109/L	150 - 350
Leukocytes		109/L	4.5 - 11
Eosinophils		109/L	0 – 0.4
Basophils		109/L	0 – 0.15
Monocytes		109/L	0.18 – 0.5
Hematocrit	M	Ratio	0.41 -0.53
Hematocrit	F	Ratio	0.36 – 0.46
Erythrocytes	F	1012/L	4 – 5.2
Erythrocytes	M	1012/L	4.5 -5.9
INR		ratio	0.8 -1.2

Based on Kratz et al.(4)

Table 7 - Generic ranges for biochemistry parameters

Test	Unit	Lower – Upper limit of normal
Albumin	g/L	35 - 55
BUN	mmol/L	3.6 – 7.1
Calcium	mmol/L	2.2 - 2.6
Chloride	mmol/L	80 - 115
Corrected calcium	mmol/L	2.2 – 2.6
Glucose	mmol/L	3.9 - 7
Bicarbonate (HCO ₃)	mmol/L	22 - 29
Carbon dioxide	mmol/L	21 - 30
Potassium	mmol/L	3.5 - 5
Magnesium	mmol/L	0.8 - 1.2
Sodium	mmol/L	136 - 145
Phosphate	mmol/L	1 - 1.4
Protein	g/L	55 - 80
Urea	mmol/L	3.6 - 7.1

ACT15319 16.1.9 Statistical analysis plan

ELECTRONIC SIGNATURES

Signed by	Meaning of Signature	Server Date (dd-MMM-yyyy HH:mm)

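### The SAP's corrected-calcium formula uses a coefficient about four times too large for calcium in mmol/L, so corrected-calcium results are misclassified whenever albumin is far enough from 40 g/L

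*SAP*

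**What the plan says.** SAP 2.5.1 (General conventions) lists the formulas for derived parameters. The result is labelled "Corrected Calcium (mmol/L"), the main term is "Serum Calcium (in mmol/L)} + 0.8 (4", and the quantity subtracted inside the bracket is "serum albumin [in g/dL"]. All three units are therefore explicit. No other section of either document gives a different coefficient or a version in mg/dL.

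SAP Appendix A, Table 7 ("Generic ranges for biochemistry parameters"), has one row reading "Calcium mmol/L 2.2 - 2.6" and a separate row reading "Corrected calcium mmol/L 2.2 – 2.6". The same table gives albumin a normal range of 35 to 55 g/L.

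SAP 2.4.6.4 states: "Each laboratory test result will be graded by CTCAE criteria (version 4.03), when applicable". It assigns the sponsor's generic ranges to the parameters listed in Tables 6 and 7 and reports the worst on-treatment grade per patient. SAP 2.1.4.5 adds: "Clinical laboratory values will be converted into standard international units that will be used in all listings and tables".

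**The concern.** The coefficient and the calcium unit do not belong together. A coefficient of 0.8 with albumin in g/dL is dimensionally reasonable if calcium is in mg/dL. Here it is added directly to a value in mmol/L, where the whole normal range spans 0.40.

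If the formula is programmed as written, a patient whose measured calcium is normal can be reported high when albumin is below 40 g/L and low when it is above. The reverse also happens: low albumin can lift a truly low corrected value into range, and high albumin can pull a truly high one down into range.

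Laboratory abnormalities form part of the Phase 1 primary safety endpoint and of the secondary safety endpoint in the protocol summary. Chemistry abnormalities are also in each cohort's interim output (SAP section 3). Because the worst grade per patient is taken, and SAP 2.5.5 lets unscheduled tests count, a single visit with albumin away from 40 g/L is enough to create a false abnormality.

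**Working it through.** **Inputs from the SAP.** Coefficient 0.8, calcium in mmol/L, albumin in g/dL with reference value 4 (2.5.1). Normal calcium and corrected calcium 2.2 to 2.6 mmol/L; normal albumin 35 to 55 g/L, that is 3.5 to 5.5 g/dL (Table 7).

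**Assumptions not in the documents.** The molar mass of calcium is 40.08 g/mol, a physical constant. The coefficient 0.8 is taken to have been meant for calcium in mg/dL.

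**Step 1, internal check using only the SAP's figures.** Shift = 0.8 × (4 - albumin).
- Albumin 3.5 g/dL: 0.8 × 0.5 = +0.40 mmol/L.
- Albumin 5.5 g/dL: 0.8 × (-1.5) = -1.20 mmol/L.
- Width of the corrected-calcium range: 2.6 - 2.2 = 0.40 mmol/L.

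Normal variation in albumin alone thus moves the result by up to three times the width of the normal range.

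**Step 2, unit conversion.** 1 mg/dL = 10/40.08 = 0.2495 mmol/L, so 0.8 mg/dL = 0.8 × 0.2495 = 0.1996 mmol/L, about 0.2. The ratio is 0.8/0.1996 = 4.01.

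**Step 3, worked values** (range 2.2 to 2.6 mmol/L).

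| Calcium, mmol/L | Albumin, g/L | As printed (0.8) | With 0.2 |
|---|---|---|---|
| 2.4 | 35 | 2.80, high | 2.50, in range |
| 2.4 | 40 | 2.40, in range | 2.40, in range |
| 2.4 | 45 | 2.00, low | 2.30, in range |
| 2.4 | 55 | 1.20, low | 2.10, low |
| 2.2 | 35 | 2.60, in range | 2.30, in range |
| 1.9 | 35 | 2.30, in range | 2.00, low |
| 2.9 | 45 | 2.50, in range | 2.80, high |

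Converting calcium to mg/dL, adding 0.8 × (4 - albumin) and converting back agrees with adding 0.02 × (40 - albumin in g/L) to three decimals in the six pairs tested.

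**Step 4, how far albumin may move.** Calcium of 2.4 leaves the range when the shift exceeds 0.2. As printed, that takes 0.2/0.8 = 0.25 g/dL, so the result stays in range only for albumin 3.75 to 4.25 g/dL. With 0.2 it takes 0.2/0.2 = 1.0 g/dL, so it stays in range for 3.0 to 5.0 g/dL.

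**Step 5, illustrative share misplaced.** Suppose measured calcium is uniform over 2.2 to 2.6 and albumin is uniform over a stated interval. The share falling outside the range is the average of min(|shift|, 0.40)/0.40.

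| Albumin interval, g/L | As printed | With 0.2 |
|---|---|---|
| 35 to 45 | 50% | 13% |
| 35 to 55 | 75% | 31% |
| 25 to 40 | 83% | 38% |

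Only the difference between the columns is due to the coefficient. CTCAE cut-offs are not reproduced in the documents, so the check is against the normal range and not grade by grade.

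**The case against.** The strongest counter-arguments concern reach, not arithmetic.

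- **Limited consequence.** This is one derived laboratory variable in a non-comparative study with descriptive safety summaries. It does not enter response rate or the Simon thresholds. DLTs are judged by investigators and the sponsor (protocol 9.1.1), and laboratory values become adverse events only through treatment changes, seriousness or special-interest status (protocol 10.5.1). This stands: no efficacy result depends on the formula, and those safety judgements do not use it.
- **Use is partly inferred.** SAP 2.1.4.5 names calcium and albumin but not corrected calcium, and 2.4.6.4 grades only where applicable. This is fair as far as it goes. However, 2.5.1 says its formulas will be used, Table 7 gives corrected calcium its own range, and 2.4.6.4 points to Table 7 for grading.
- **Measured calcium is unaffected.** This is true, and output on uncorrected calcium remains valid. It does not repair the corrected value reported beside it.
- **Not every patient is misclassified.** The error is zero at 40 g/L and small near it. Calcium 2.2 with albumin 35 g/L stays in range, and calcium 2.4 with albumin 55 g/L is low under either coefficient. This stands and limits the claim to some patients.
- **The figure 0.2 is not in the documents.** This is correct. Table 7 shows that 0.8 is untenable; the replacement rests on unit conversion.

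**Conclusion.** The formula is wrong as written. With calcium in mmol/L and albumin in g/dL, the albumin correction is 4.01 times too large. By the SAP's own ranges, its mid-normal pair of calcium and albumin is reported as low.

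The effect depends on albumin: none at 40 g/L, and for a calcium of 2.4 mmol/L a false abnormality appears once albumin departs by more than 2.5 g/L, where the converted formula needs about 10 g/L. True abnormalities can also be masked.

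The damage is confined to corrected-calcium output, at baseline, on treatment and in the interim chemistry summaries. The factor of four rests on calcium's molar mass and on 0.8 having been meant for mg/dL; the internal inconsistency with Table 7 needs neither. The percentages in Step 5 depend on assumed uniform distributions and show scale only.

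**What to change.** In SAP 2.5.1, replace 0.8 with 0.2: corrected calcium (mmol/L) = calcium (mmol/L) + 0.2 × (4 - albumin in g/dL). Preferably write it as calcium (mmol/L) + 0.02 × (40 - albumin in g/L), which uses the albumin unit in Table 7 and avoids a hidden conversion. If the g/dL form is kept, state that albumin in g/L must first be divided by 10.

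Add corrected calcium to the variable list in SAP 2.1.4.5, so that its use in grading is explicit.

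The cost is one coefficient, one added list item and one line in the derivation program. If interim tables have already been produced with the printed formula, rerun the corrected-calcium rows and record the change.

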2.5.2 Data handling conventions for secondary efficacy variables

Not applicable.

2.5.3 Missing data

The analyses and summaries of continuous and categorical variables will be based on observed data only. Percentages will be calculated using as denominator the number of patients with non-missing observation in the considered population. When relevant, the number of patients with missing data is presented.

When incomplete or missing dates were found in the eCRF, attempts were made to retrieve the complete date, especially for dates within the month prior to first dose. However, if some dates remain incomplete, the following rules will be applied:

Handling of disease characteristics missing/partial dates

- If the day is missing, it will be estimated by 1
- If the month is missing, it will be estimated by 1 (only for medical history variables)
- If the year is missing, no estimation will be performed

Handling of medication missing/partial dates

No imputation of medication (other than anti-cancer therapies) start/end dates or times will be performed. If a medication date or time is missing or partially missing and it cannot be determined whether it was taken prior or concomitantly, it will be considered a prior, concomitant, and post-treatment medication.

For prior anti-cancer therapies, following rules will be applied:

Missing/partial start date will be imputed as follows:

- If year and month exist, day is missing, impute as the first day of the month
- If only year exists, month and day are missing, impute as the first day of the year
- If year, month, and day are all missing, no imputation will be applied

Missing/partial end date will be imputed in a two-step approach as follows:

- Step 1: Use the following rule to impute end date:
 - If year and month exist, day is missing, impute as the first day of the month
 - If only year exists, month and day are missing, impute as the first day of the year
 - If year, month, and day are all missing, no imputation will be applied
- Step 2: If imputed end date is earlier than start date, set the imputed end date the same as start date

Imputation of incomplete date for post anti-cancer treatment start date

For post anti-cancer treatments, if the medication start date is missing, it will be imputed as follows:

- If the medication start day and month are missing and the medication start year is the same as treatment end year, the medication start date will be set equal to treatment end date + 1
- If the medication start day and month are missing and the medication start year is after the treatment end year, the medication start day and month will each be set to 01
- If the medication start day is missing and medication start year and month is the same as the treatment end year and month, the medication start day will be set equal to the treatment end day + 1
- If the medication start day is missing and medication start month is before the treatment end month and the medication start year is the same as treatment end year, the medication start day will be set to 01
- If the medication start day is missing and the medication start month is after the treatment end month and the medication start year is the same as treatment end year, the medication start day will be set to 01

- If the medication start day is missing and the medication start month is not missing and the medication start year is after the treatment end year, the medication start day will be set to 01
- If the medication start day, start month and start year is missing, the medication start date will be set equal to the treatment end date + 1

No imputation will be done for the missing/partial end date.

Handling of adverse events with missing or partial date of onset

Missing or partial adverse event onset dates (occurrence or becoming serious) will be imputed so that if the partial adverse event onset date information or visit number does not indicate that the adverse event started prior to treatment or after the treatment-emergent adverse event period, the adverse event will be classified as treatment-emergent. In case of AEs worsening during the study, the emergence will also be based on the cycle of worsening. No imputation of adverse event end dates will be performed. These data imputations are for categorization purpose only and will not be used in listings. No imputation is planned for date of adverse event resolution.

Handling of death with missing or partial date of death

The imputation for missing or partial death date will proceed as follows:

- If the death day is missing and the death month and year are the same as the last month and year the patient was last known to be alive, the death day will be set equal to the last day the patient was known to be alive + 1
- If the death day is missing and the death month is after the month the patient was last known to be alive and the death year is the same as the year the patient was last known to be alive, the death day will be set to 01
- If the death day and month are missing and the death year is the same as the year the patient was last known to be alive, the death date will be set equal to the date the patient was last known to be alive + 1
- If the death day and month are missing and the death year is after the year the patient was last known to be alive, the death day and month will both be set to 01

If the date the patient was last known to be alive is partial or missing, no imputation for missing or partial death date will be performed. The last date the patient was known to be alive is the last of: date of last dose, date of last visit performed (when the patient is known to be alive according to subject vital status), date of last laboratory assessment, and date of last vital signs.

Handling of AEs with missing grade

If the grade is missing for one of the treatment emergent occurrences of an AE, the maximal severity on the remaining occurrences will be considered. If the severity is missing for all the occurrences, no imputation will be done and missing grades will be summarized in the “all grades” category.

Handling of missing assessment of relationship of adverse events to investigational medicinal product

If the assessment of the relationship to the regimen is missing, then the relationship to the regimen has to be assumed and the adverse event considered as such in the frequency tables of possibly related adverse events, but no imputation should be done at the data level. No imputation will be done for relationship to NMIP.

Handling of parameters expressed as inequality or approximation

For some parameters (such as laboratory parameters), if the value is expressed as “< xx”, “≤xx”, half of the numeric portion of the entry or limit of quantification will be used in calculations.

Handling of missing date/time in duration of infusion calculation

When both REGN2810 and isatuximab are given to a patient on the same visit:

- Missing REGN2810 end date/time will be imputed by isatuximab start date/time (if available)
- Missing isatuximab start date/time will be imputed by REGN2810 end date/time (if available)

Other types of missing date/time will not be imputed, and data will be excluded from the analysis of duration of infusion.

Handling of other missing dates

Incomplete date of cancer diagnosis:

- If the day of the cancer diagnosis is missing, the date will be imputed to the first day of the month
- If day and month of the cancer diagnosis are missing, no imputation will be done

Incomplete date of progression for the last prior regimen:

- If the day of the progression for the last prior regimen is missing, the date will be imputed to the end day of the month
- If day and month of the progression for the last prior regimen are missing, no imputation will be done

Incomplete date of prior surgery:

- If the day of the last prior surgery is missing, the date will be imputed to the end day of the month
- If day and month of the last prior surgery are missing, no imputation will be done

Incomplete date of prior radiotherapy:

- If the day of the last prior radiotherapy is missing, the date will be imputed to the end day of the month

If day and month of the last prior radiotherapy are missing, no imputation will be done.

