- Progression-free survival: For mCRPC patients, PFS is defined as the time from first study treatment administration to the date of first documented disease progression or the date of death from any cause, whichever occurs first. Disease progression includes radiographic disease progression (per PCWG3 criteria) or unequivocal clinical progression. For NSCLC patients, PFS is defined as the time from first study treatment administration to the date of first documented radiographic progression (per RECIST 1.1) or the date of death from any cause, whichever occurs first

For patients who did not experience documented disease/radiographic progression or death before the analysis cut-off date or the date of initiation of new anticancer treatment, PFS will be censored at the date of the last valid disease/radiographic assessment not showing disease progression performed prior to initiation of a further anticancer treatment or the analysis cut-off date, whichever comes first. In addition, patient without PFS event (death or documented disease/radiographic progression) and without any valid post-baseline disease assessments will be censored at the day of first treatment (Day 1)

- Disease control rate (DCR): DCR is defined as the proportion of patients with confirmed complete response (CR) or partial response (PR) or stable disease (SD), as assessed by Investigator (per PCWG3 criteria for mCRPC patients and per RECIST 1.1 criteria for NSCLC patients) relative to the total number of patients in the analysis population

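### Incomplete next-therapy start dates are imputed to the earliest possible day with no floor at documented progression, so some real PFS and DOR events can become censored observations

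*SAP*

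**What the plan says.** SAP 2.5.3 imputes incomplete start dates of anticancer therapy given after study treatment as follows:

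- Day missing, same month and year as treatment end: "the medication start day will be set equal to the treatment end day + 1".
- Day missing, later month or later year: day 01 of the recorded month (one such rule begins "If the medication start day is missing and the medication start month is after the treatment end month").
- Day and month missing, same year as treatment end: "the medication start date will be set equal to treatment end date + 1".
- Day and month missing, later year: "the medication start day and month will each be set to 01".
- Everything missing: "the medication start date will be set equal to the treatment end date + 1".

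The section says that before imputation "attempts were made to retrieve the complete date", with particular stress on dates in the month before first dose. It does not define treatment end date.

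SAP 2.1.3.2 counts progression or death as a PFS or DOR event only if it precedes the cut-off and any further anticancer therapy. Otherwise the patient is censored at the last valid assessment "not showing disease progression performed prior to initiation of a further anticancer treatment". A PFS patient with no event and no valid post-baseline assessment is censored at Day 1. SAP 2.1.3.1 excludes assessments made after further therapy starts from best overall response.

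**The concern.** The imputed date decides whether a progression counts. In a patient who stops study treatment because a scan shows progression, the order is last dose, progression scan, next therapy. Each rule places an incomplete therapy start as early as the recorded information allows, which can be before the scan. The progression then appears to follow new therapy and is replaced by censoring at an earlier assessment.

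This censoring is informative, because it removes events from patients known to have progressed. Kaplan-Meier PFS and DOR move upward.

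Nothing else in the SAP prevents this. Section 2.5.2, on data handling for secondary efficacy variables, is marked not applicable. The AE-date imputation in 2.5.3 is restricted to categorisation, but the therapy-date imputation carries no such restriction.

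**Working it through.** The plan gives no figure on this point, so there is none to reproduce. I applied the rules literally, reading treatment end as the date of last dose (an assumption).

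**Schedule.** Cycles are 21 days (protocol 1.2 and 1.3). Scans are every 9 weeks from the end of Cycle 3, day 63 ±7 (protocol 1.3). The first scan therefore falls about three weeks after the Cycle 3 dose.

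**Worked case.** First dose 22 April 2019; doses on 13 May and 3 June; progression scan on 22 April + 63 days = 24 June.

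| True next-therapy start | What is recorded | Imputed start | 24 June progression |
|---|---|---|---|
| 28 June | month and year | 4 June | lost |
| 28 June | year only, or nothing | 4 June | lost |
| 10 July | month and year | 1 July | kept |
| 10 July | year only, or nothing | 4 June | lost |

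In the lost cases the imputed start is 20 days before the scan. With no earlier post-baseline scan, PFS is censored at Day 1.

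**Share of incomplete dates that lose the event.** I simulated 100,000 patients per scenario, with a random calendar start and progression at the first, second or third scan (±7 days). An event is lost if the imputed start precedes progression. The gap from progression to next therapy is an assumption and is varied.

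| Gap (days) | Day missing | Day and month missing | All missing |
|---|---|---|---|
| 1–14 | 67% | 91% | 93% |
| 7–28 | 37% | 89% | 93% |
| 14–42 | 14% | 86% | 94% |
| 30–60 | 0% | 81% | 93% |

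These rows are for patients who stop at first progression. For patients dosed up to confirmation, the loss is 0% in every cell: PFS and DOR use the first progression date, and the last dose is on or after it.

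The last column can be checked by hand. Of the 15 scan offsets from −7 to +7 days, only +1 puts the last dose on the day before the scan. The imputed start then equals the progression date and the event is kept, so the loss is 14/15 = 93.3%. In the day-missing column, a gap of at least 30 days means that even day 01 of the recorded month cannot precede progression.

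**Events lost per cohort.** Lost = n × 0.8 × q × L. Here n is 49 (mCRPC) or 36 (NSCLC), from protocol Table 8. The other inputs are assumptions: 80% of patients have a PFS event; q, the share of those whose therapy date stays incomplete, is 2% to 20%; and L, the share of such dates that lose the event, is 50%.

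- n = 49: 49 × 0.8 × 0.02 × 0.5 = 0.4, up to 49 × 0.8 × 0.20 × 0.5 = 3.9.
- n = 36: 36 × 0.8 × 0.02 × 0.5 = 0.3, up to 36 × 0.8 × 0.20 × 0.5 = 2.9.

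**Effect on 6-month PFS.** A second simulation (1,500 runs per scenario) assumed 49 patients, latent median PFS of 100 days, dosing to the progression scan, and 70% of patients starting new therapy 1 to 6 weeks after progression. About 25% to 27% of partial dates lost the event. With 10%, 20% and 30% partial dates, mean events lost were 0.92, 1.74 and 2.59. Six-month PFS rose from 39.6% to 40.4%, 40.8% and 41.1%, a shift of 0.8 to 1.5 points. For scale, the binomial standard error is √(0.396 × 0.604 / 49) = 0.070, or 7 points.

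**The case against.** The strongest case on the other side is that few dates will be affected and little follows from them. Imputation comes only after attempts at retrieval. Protocol 12.4 brings the end-of-treatment visit forward when a patient starts another anticancer therapy, and new therapy is recorded there, so the early starts most likely to delete an event are also the ones most likely to be fully dated. Treatment may continue past first progression until confirmation if the patient is stable (protocol 6.7.1), and those patients lose nothing. If treatment end meant the end-of-treatment visit, the + 1 rules would do less harm, although the day-01 rules could still precede progression. PFS and DOR are descriptive, and the shift is small beside sampling error. All of this stands, and it limits the size of the problem. It does not remove the mechanism.

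A further objection is that a floor at progression uses the outcome to set the therapy date and can err the other way. That also stands, and it is why the current rule should remain as a sensitivity analysis.

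A reader might infer that every response and duration measure is inflated. The documents do not support that:

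- Duration of SD enters only through DCR ≥6 months (SAP 2.1.3.3). If progression at day 189 is deleted, SD is censored at about day 126 and the patient leaves the numerator, so the bias is downward.
- Cutting off best overall response cannot create a confirmed response. It can only drop a confirmatory assessment, which lowers the response rate.

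**Conclusion.** The point holds for PFS and DOR. Followed as written, SAP 2.5.3 and 2.1.3.2 can turn a documented progression into a censored observation in a patient who stops at first progression, when the next therapy falls in the same month or when its month or whole date is missing. The direction is upward for these two Kaplan-Meier endpoints.

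The likely size is roughly 0 to 4 events per cohort and about 1 point on 6-month PFS. This rests on treatment end meaning last dose and on assumed values for the frequency of incomplete dates, the gap to next therapy and the proportion with events. None of these is in the documents.

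It would go too far to say that events are lost in all patients who progress and move on, since those dosed past first progression or with complete dates are unaffected. Nor does the upward bias reach the Simon decision, which uses response rate. The change is worth making because it is cheap and removes an avoidable source of informative censoring in small cohorts.

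**What to change.** In SAP 2.5.3:

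1. Define treatment end date.
2. Impute the start of further anticancer therapy as the later of the value under the current rules and the first documented progression date + 1 day, provided this stays within the recorded month or year. Apply the same rule when the date is wholly missing.
3. Repeat PFS and DOR under the current rule as a sensitivity analysis.

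Where therapy truly began after the day of progression, the floored date always falls after progression, so no such event is lost. In the worked case the 24 June event is kept.

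The cost is about a sentence of SAP text and a small programming change. The downside is that a patient who truly switched before progression within the same partial period would be counted as an event; the sensitivity analysis shows how much that matters. The floor does not restore a confirmatory assessment dropped from best overall response in a patient with no documented progression.
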